6.3.3 Final Outcomes and Determination of Allergy Status

If vital signs (including peak flow) and focused PE are within reasonable limits after the applicable observation periods, subjects will be counseled that they do not have an allergy to PCN (B-lactams). They will be provided with written documentation that they will be encouraged to share with their medical providers, including the STD clinic and their primary care physician (if they have one).

Final outcomes of the oral challenge will be recorded on a CRF as no reaction (negative), reaction (positive) or unevaluable (if the participant leaves the clinic before the applicable observation period is completed). If there is a reaction, after providing standard treatment, study staff will record the type of reaction, severity and how long after the amoxicillin was administered it occurred on the oral challenge testing results CRF.

If reactions to the amoxicillin oral challenge occur, they will be graded and documented using the Toxicity Table (Appendix C).

Rarely, an oral challenge in an individual who skin tests negative can produce an acute reaction (e.g., anaphylaxis) requiring emergency care. Unexpected reactions that place a subject at increased risk will be treated as necessary and reported to the IRB and DMID as required.

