2.2.2 Development of Algorithms to Increase Use of B-lactams

Chiriac²² recently reviewed the standardized drug allergy algorithms that were promulgated during the 2018 International Drug Allergy Symposium. These incorporated multiple algorithms, including large experiences from the Massachusetts General Hospital/Partners Health, Dartmouth, Mayo Clinic, Jacksonville, Rush University, University of Nebraska, University of Texas and groups from the UK and other systems. The authors noted that most patients report low risk allergy histories and, thus, many B-lactams are likely safe for use. Furthermore, standardized allergy algorithms can be used by trained personnel beyond allergy specialists, including medical doctors from other specialties, advanced practitioners, and pharmacists. The consensus algorithms included a series of elements:

- Definition of high-risk and low-risk phenotypes.
- Clinical practice guidelines for patients who had mild reactions were to use a different generation cephalosporin, to perform a test dose procedure or to provide access to skin testing.
- Recommendation to go directly to an oral challenge test dose without skin testing for low-risk patients whose reported “allergy” was more consistent with a non-allergic reaction (e.g., mild gastrointestinal (GI) distress). These algorithms are being increasingly adopted.

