2.2.3 Oral Challenge Approaches

The approaches recommended in the increasingly used algorithms, in many cases, advise bypassing skin testing and going directly to an oral challenge in low-risk patients. Two recent studies evaluated the impact and safety of this approach.

Iammatteo²³ instituted a direct oral challenge procedure in drug allergy clinics at Montefiore Hospital in the Bronx, NY. This study enrolled subjects >7 years old with non-life-threatening reported reactions to PCN. The exclusions included bronchospasm, anaphylaxis, non-IgE syndromes such as Stevens Johnson, cutaneous and/or mucosal blisters, hypersensitivity vasculitis, nephritis, hepatitis or anemia. Of 165 patients screened, 159 were enrolled and 156 completed a graded challenge without skin testing but which also incorporated a placebo. Of those challenged, 19 had reactions of which only 4 were determined to be allergy mediated and all were mild. It should be noted that this study skipped skin testing entirely.

Macy instituted a large PCN allergy management protocol at Kaiser Permanente San Diego.³ Between January 2017-December 2018, 806 patients had a direct oral challenge (no skin testing). Of these patients, 2 (0.2%) had an acute reaction, 9 (1.1%) had a delayed reaction; all were managed on-site with oral antihistamines or IM epinephrine; there were no hospitalizations. An additional 23 subjects (2.9%) had subjective reactions, such as mild nausea or headache.

Similarly, Blumenthal²⁴ implemented a risk-based algorithm in a large Boston based health system, and in a small study, directly challenged 83 low-risk patients in an outpatient setting. Of these patients, 3.6% experienced an immediate reaction (hives and rash), all resolved with treatment. In a larger antimicrobial stewardship-oriented intervention²⁵ which was performed in 5 acute care hospitals in 2016-17, patients with prior B-lactam allergy histories were evaluated using an EMR-based decision support tool and allergist consultation. A test dose of the prescribed B-lactam was administered in 1,045 instances to 942 patients with allergy histories considered low-risk. 96% of these cases did not have skin tests. Forty (3.6%) of patients had hypersensitivity reactions, 14 of which occurred within an hour of dosing. All were minor and treated successfully. Reactions were most frequent with late generation cephalosporins.

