7.1.3 Oral Challenge

Pregnancy status will be verified. Pregnant women will not be enrolled in the DOC group.

Prior to the oral challenge, vital signs will be recorded (heart rate, respiratory rate, blood pressure and peak flow). A focused PE will be performed (eyes, pharynx, lungs and skin). Subjects will be observed for 60 minutes \pm 10 minutes after the amoxicillin is administered. Vital signs, peak flow measurement and focused PE will be repeated after the 60-minute observation period \pm 10 minutes.

After oral challenge, subjects will be assessed for the most common elicited reactions associated with amoxicillin which will be graded and documented using the Toxicity Table (Appendix C):

- Cardiovascular: lightheadedness, loss of consciousness
- Skin: urticaria, flushing, rash, angioedema
- HEENT: conjunctivitis, rhinitis, congestion
- Respiratory: shortness of breath, wheezing
- GI: nausea, vomiting, diarrhea

Data will be collected on reactions to amoxicillin as a diagnostic tool for defining an allergic reaction that was not identified by the skin testing. Unanticipated reactions that place the subject at increased risk will be recorded on the AE CRF and reported to the IRB and DMID according to their reporting guidelines.

Subjects will be provided with contact information for study staff to report the development of additional symptoms.

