7.3 Analysis of Primary Objective

The primary analysis will be performed on the Treated population and Per Protocol population. Estimates with corresponding exact (Clopper-Pearson) 95% confidence intervals for the following measures will be provided:

- The prevalence of PCN reactivity validated either by skin test or by direct oral challenge among those participants who report a history of PCN (B lactam) allergy and who have low-risk histories.
- The NPV on true PCN (B-lactam) allergy of the algorithm / PCN (B-lactam) allergy history screening questionnaire performance in the Treated population.

The NPV for each low-risk allergy item listed on the questionnaire will be estimated and will be compared with the prevalence of PCN reactivity using exact test of binomial proportion. The p-values will be adjusted with Benjamini-Hochberg procedure.

To construct a short standardized post-study questionnaire (4-6 questions) from the PCN (B-lactam) allergy history screening questionnaire, we will first use the item-characteristic curve from Item Response Theory (IRT) to evaluate each question item's discrimination ability of true PCN (B-lactam) allergy and use variable importance evaluation functions to indicate which questions are most useful for predicting the true PCN (B-lactam) allergy. Based on the results of IRT and variable importance analyses, we will then apply machine learning approaches such as random forest (Svetnik et al., 2003) via R package caret, to select a short post-study questionnaire that has the highest NPV among those possible short questionnaires with 4-6 selected questions.

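### The primary endpoint has no rule separating an allergic challenge reaction from drug intolerance, and the protocol's two rules for a negative challenge can disagree for the same subject

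*Protocol*

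**What the plan says.** **Scoring.** Protocol 6.3.3: "Final outcomes of the oral challenge will be recorded on a CRF as no reaction (negative), reaction (positive) or unevaluable". No minimum grade, hypersensitivity criterion or adjudication step comes before positive.

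**What is called a reaction.** Protocol 6.3.1 and 6.3.2 list symptoms that a subject may report while waiting, among them abdominal pain, nausea and vomiting, and tell staff to record these reactions with the final assessment. The list in 7.1.3 of elicited reactions to be graded includes "GI: nausea, vomiting, diarrhea". Appendix C grades transient abdominal cramps as mild.

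**A second rule.** Protocol 6.3.3 also says: "If vital signs (including peak flow) and focused PE are within reasonable limits after the applicable observation periods, subjects will be counseled" that they have no allergy to penicillin or B-lactams. Section 6.3.1 gives the same rule for the PST group. What counts as acceptable is not defined.

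**Purpose.** Protocol 7.1.3 says the reaction data serve to define allergic reactions that the skin test missed, but gives no rule for doing so.

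**Analysis.** SAP 7.3 estimates the prevalence of reactivity by skin test or challenge and "The NPV on true PCN (B-lactam) allergy of the algorithm" and questionnaire, then selects 4 to 6 questions that predict true allergy. It defines neither reactivity nor true allergy. SAP 7.5 tabulates reaction type and severity without linking them to the primary endpoint.

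**Background.** Protocol 2.2.2 describes a reported history that "was more consistent with a non-allergic reaction (e.g., mild gastrointestinal (GI) distress". Section 2.2.3 separates allergic from other reactions in two cited series: "19 had reactions of which only 4 were determined to be allergy mediated" (of 156 challenged), and, in 806 direct challenges with 2 acute and 9 delayed reactions, "An additional 23 subjects (2.9%) had subjective reactions, such as mild nausea or headache".

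**The concern.** Both primary outcomes and the short questionnaire rest on one label per subject. Followed as written, that label can turn positive because of a symptom that the protocol's own background would not call allergy. In a group where allergy is expected in a few per cent at most, a small number of such symptoms can match or exceed the true positives. Prevalence is then overstated, NPV understated, and the questionnaire trained partly on intolerance.

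The two rules also diverge for an identifiable subject: nausea only, with normal vital signs, peak flow and examination. Under one sentence of 6.3.3 that subject is told there is no allergy; under another the form can say positive. Protocol 6.4 has results given in writing and passed to the clinic, so the two statuses can coexist in the record. If the choice between them is left until analysis, it is made with the data in view.

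**Working it through.** **1. The rules side by side, for a subject with nausea only**

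| Source | Basis | Result |
|---|---|---|
| Protocol 6.3.3, CRF outcome, with 6.3.1/6.3.2 use of the word reactions | Symptom reported | Positive |
| Protocol 6.3.1 and 6.3.3, counselling | Vital signs, peak flow and examination acceptable | Not allergic |
| SAP 7.3 | Reactivity and true allergy, undefined | Not determined |

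**2. The plan's own sample size**

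Inputs from Protocol 8.2: sensitivity Se = 0.85, specificity Sp = 0.95, prevalence p = k = 0.03, target bound L = 0.984, power 85%, alpha 5%, and 5% higher-risk and not tested.

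- NPV = Sp(1−p) / [Sp(1−p) + (1−Se)p] = 0.9215 / (0.9215 + 0.0045) = 99.51%.
- φ1 = (1−Se)/Sp = 0.15/0.95 = 0.1579. φ0 = [(1−L)/L]·[(1−p)/p] = (0.016/0.984)(0.97/0.03) = 0.5257.
- V = Se/[(1−Se)k] + (1−Sp)/[Sp(1−k)] = 188.89 + 0.05 = 188.94.
- n = (1.645 + 1.036)² · V / [ln(φ0/φ1)]² = 7.189 × 188.94 / 1.447 = 938.8, with one-sided alpha.
- 938.8 / 0.95 = 988.2, which matches the stated 988. About 939 subjects are therefore tested.

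**3. How few positives the target tolerates**

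Take NPV as 1 − (positives / tested) among low-risk subjects, because higher-risk subjects are not tested. Use the two-sided exact (Clopper-Pearson) interval of SAP 5 and 7.3, with n = 939.

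- 7 positives: lower bound 98.47%, above 98.4%.
- 8 positives: lower bound 98.33%, below 98.4%.

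So at most 7 positives are allowed. With a true-allergy rate of 0.49% (1 − 0.9951) plus an added rate q of non-allergic reactions scored positive, the chance of 7 or fewer is binomial:

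| q | Expected positives (939 × rate) | P(lower bound > 98.4%) |
|---|---|---|
| 0 | 4.6 | 91% |
| 0.5% | 9.3 | 29% |
| 1% | 14.0 | 3% |

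With a one-sided 95% bound, up to 8 positives are allowed and the chances are 96%, 42% and 6%. The pattern is the same.

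**4. How large q might be, from the series in Protocol 2.2.3**

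| Series | Any reaction | Narrower count |
|---|---|---|
| Graded challenge, n = 156 | 19/156 = 12.2% | Allergy-mediated: 4/156 = 2.6% |
| Direct challenge, n = 806 | (2+9+23)/806 = 34/806 = 4.2% | Acute plus delayed: 11/806 = 1.4% |

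The ratios are about 5 (19/4) and 3 (34/11). Carried to 939 subjects, the exact lower NPV bounds are 85.6% against 96.2% in the first series (114 and 24 positives), and 94.2% against 97.6% in the second (40 and 13). All four lie below 98.4%.

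**The case against.** The best reply is that no sentence says nausea is scored as allergy. The word reaction is not formally defined; 6.3.3 offers an objective rule based on vital signs and examination; and 7.1.3 states an intention to identify allergic reactions. The challenge CRF and the Manual of Procedures are not among the documents and may carry scoring instructions. This stands as far as it goes: the defect is an undefined and inconsistent endpoint, not proof that every symptom will be counted. It does not remove the defect, because 6.3.1 and 6.3.2 do apply the word to reported symptoms and the SAP, where the endpoint should be fixed, is silent.

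Three stronger readings are tempting, and the documents do not support them.

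- *The endpoint measures intolerance rather than allergy.* It also counts skin-test positives in the PST group and genuinely allergic reactions, so it is a mixture.
- *The protocol elsewhere treats light-headedness and pulse change as non-allergic.* The nearest history items in 6.1.2.1, dizziness and palpitations, are higher-risk. The low-risk list is not a list of non-allergic symptoms either, since it includes rash and older hives. Only mild GI distress is called non-allergic, and that concerns history.
- *The study's conclusion flips on this rule alone.* In the 156-patient series neither coding reaches 97% or 98.4%. In the 806-patient series the narrower coding passes 98.4% only if the 9 delayed reactions are dropped. Moreover, 97% is the useless-test value at an assumed 3% prevalence and moves with prevalence, and neither document makes 98.4% a formal pass mark.

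It is also fair to say that over-calling lowers NPV, which is the cautious direction, and that the data needed for a definition are already collected. The first point does not help the questionnaire, whose training label would still be contaminated. The second is why the repair is cheap.

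**Conclusion.** The concern holds in this form: the plan lets any challenge reaction count as positive for the primary prevalence, the NPV and the questionnaire outcome, gives no criterion for hypersensitivity, and contains a second rule that can give the same subject the opposite status. It should be settled before the data are frozen.

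The size depends on how often non-allergic symptoms arise and how sites score them, which the documents do not give. The calculation at the planned NPV borrows no reaction rate from other studies: an extra 0.5% to 1% of subjects, roughly 5 to 9 of 939, is enough to make the planned 98.4% bound unlikely. It assumes 939 tested, a 0.49% true rate and the exact two-sided interval.

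The cited-series rates are illustrative only. They come from direct challenge, the first series included a placebo step, and the timing of the subjective reactions is not stated. Delayed reactions may fall outside a 30 to 60 minute observation. About half of this trial's subjects are challenged only after a negative skin test.

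**What to change.** **SAP 7.3, before data freeze.** From the type, severity and onset time already recorded on the challenge CRF and graded with Appendix C, derive two categories: reaction consistent with hypersensitivity, and other reaction or intolerance. Write down the classification rule, including borderline cases. Count as positive only the first category, plus skin-test positives in the PST group, for the primary prevalence, the NPV and the questionnaire outcome. Report any reaction counted as positive as a sensitivity analysis.

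**Protocol 6.3.1, 6.3.3 and 7.1.3.** Reconcile these so that the recorded outcome and the status a subject is told agree. Which clinical rule should govern is for the investigators; this point proposes none.

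**Cost.** SAP wording, one derived variable and a short reconciliation of protocol text, with no new data collection. The small downside is that borderline reactions need a classification agreed in advance; the sensitivity analysis shows how much depends on it.

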6.3.4 Managing STD Treatment and Oral Challenge

In some cases, subjects will require treatment for STDs at the visit with medications which may have side effects. This could confound the results from the oral challenge. If there are concerns, the clinicians may opt to delay administration of therapy until after the oral challenge is completed in the clinic or provide STD treatment, administer the PCN (B-lactam) allergy history screening questionnaire, perform the skin test and have the subject return to clinic for the oral challenge within 6 weeks of the clinic visit.

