This study will assess reported PCN (B-lactam) allergy. Although the ultimate goal is to optimize therapy for patients with syphilis and gonorrhea who report PCN allergy, for this study patients attending the clinic venues for any reason (visit or diagnosis) will be eligible.

We recognize that clinics have operational and throughput concerns. Since we are assessing allergy issues only, the procedures outlined in this protocol can be conducted at any time during the clinic visit, including after treatment has been administered. Usual clinical management, including treatment and partner services, will not be modified because of the study.

At some clinic visits, subjects may require treatment for STDs with medications that could confound the evaluation of the oral challenge test results. In these cases, the clinicians may opt to either delay administration of therapy in the clinic until after the oral challenge is completed or provide STD treatment, administer the PCN (B-lactam) allergy history screening questionnaire, perform the skin test and then ask the subject to return to the clinic within the next 6 weeks for the oral challenge.

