- d. Drug reaction eosinophilia and systemic symptoms (*rash with eosinophilia and organ injury*)
- e. Acute generalized exanthem (*rash with pustules*)
- f. Dystonia or muscles became very stiff or very weak
- g. Serum sickness (*rash with joint pain, fever, myalgia*)
- h. Anemia

- i. Documented drug fever
- j. Erythema multiforme (*rash with target lesions*)
- k. Hives (5 years or less)

7) What treatment did you receive for the allergic reaction on the day it started? (OK to select more than one)

- a. No treatment
- b. Went to the hospital emergency room or urgent care center
- c. Was admitted to the hospital
- d. Given epinephrine / adrenaline
- e. Given steroid pills or injections
- f. Given a steroid cream
- g. Given an antihistamine (anti-itch pill)
- h. Antibiotic discontinued
- i. Fluids through a vein
- j. Other (please list) _____
- k. Unknown

8) Did you stop taking the antibiotic or did you finish the course?

- a. Stopped after the reaction started
- b. Continued to take the antibiotic after the reaction
- c. Don't remember

9) Since you had the antibiotic reaction, have you ever taken any of the following antibiotics?

- a. Amoxicillin/Clavulanate (Augmentin)
- b. Cephalexin (Keflex)
- c. Ceftriaxone (Rocephin)
- d. Benzathine Penicillin (Bicillin) (injections)
- e. Cefuroxime (Ceftin)
- f. Cefadroxil (Duricef)
- g. Ampicillin
- h. Amoxicillin
- i. Cefaclor (Ceclor)
- j. Cefixime (Suprax)
- k. Any other drug whose name ended with "cillin"
- l. Any other drug whose name started with "cef"
- m. Other (Please list) _____
- n. Don't know or remember

10) Since you had the antibiotic reaction, have you ever been treated for gonorrhea, syphilis or strep throat?

- a. Yes (please list medication) _____
- b. No

Section 2: Skin Testing History

Questions to ask before skin testing is performed

- 11) Have you ever been skin tested for allergy to penicillin?
 - a. Yes (if Yes, go to Q12; otherwise skip to Q13)
 - b. No
 - c. Unknown

- 12) What were the results of the skin test?
 - a. Positive
 - b. Negative
 - c. Unknown

- 13) In the past week have you taken any of the following medications, including over the counter (OTC)? (***Include only medications that you have taken orally, no skin or eye medications***)
 - a. OTC cough and cold remedies containing antihistamines
 - b. Benadryl
 - c. Non-sedating antihistamines (Zyrtec, Allegra, Claritin, Xyzal)
 - d. Antivert / meclizine, Dramamine and Phenergan
 - e. Hydroxyzine (Atarax/Vistaril)

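### Appendix B Q9 and Q10 set no cut-off before today, so an STD drug given earlier in the same visit can be recorded as past exposure in two candidate items for the short form

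*Protocol*

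**What the plan says.** Two places in the protocol allow treatment first and the questionnaire second. Section 6.3.4 lets clinicians "provide STD treatment, administer the PCN (B-lactam) allergy history screening questionnaire, perform the skin test and have the subject return to clinic" for the challenge. Section 4.1 describes the same option and says more generally that study procedures "can be conducted at any time during the clinic visit, including after treatment has been administered". It adds: "Usual clinical management, including treatment and partner services, will not be modified because of the study".

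The history questionnaire (Appendix B) then asks, in Q9, "Since you had the antibiotic reaction, have you ever taken any of the following antibiotics". The options include "Ceftriaxone (Rocephin" and "Benzathine Penicillin (Bicillin) (injections", both of which are STD treatments. Q10 asks "Since you had the antibiotic reaction, have you ever been treated for gonorrhea, syphilis or strep throat" and requests the drug name on a yes. Neither item asks for a date.

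The questionnaire as a whole is the source of the short form. SAP 7.3 opens that step with "To construct a short standardized post-study questionnaire (4-6 questions) from the PCN (B-lactam) allergy history screening questionnaire" and goes on to item response theory, variable importance and random forest. Protocol 8.4.1 describes the same step and also plans an NPV for every question. Neither document removes Q9 or Q10 from the candidates or says how same-visit treatment is to be handled.

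**The concern.** Q9 and Q10 are useful as predictors only if a yes means that the subject met a B-lactam, or was treated for one of these infections, at some time after the reaction and before presenting. Protocol 2.1 reports that other investigators counted earlier B-lactam use as a low-risk marker. A dose given shortly before the question is asked carries no such information. It reflects today's diagnosis and the order in which that clinic works.

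The short form is meant to inform a decision about using a B-lactam, so in practice it would be answered before treatment. Answers collected after treatment do not represent that use. If some yes answers come from today's drug, the item may look weaker or stronger than it is, and the choice of 4-6 questions could turn on that.

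**Working it through.** No figure in the plan states this effect, so there is none to reproduce. The check is mainly a reading of the texts side by side.

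**1. Is the order allowed?** Yes, in Protocol 4.1 and 6.3.4. Section 6.1 also lets screening take place before, during or after the clinic visit, and 4.1 lets sites give the questionnaire by telephone. Some subjects can therefore answer before treatment and others after it.

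**2. Does the wording exclude today?** No. Both look-back windows run from the index reaction to the moment of asking. Q13, by contrast, limits its window to the past week, so the instrument does bound recall elsewhere.

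**3. Which drugs can trigger a yes?**
- Q9: the named options are B-lactams, with a free-text line for others.
- Q10: any drug given for the three infections, B-lactam or not.

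**4. Which analyses use the answers?**
- Low-risk or higher-risk classification (Protocol 6.1.2.1) rests on the symptom and history lists. Q9 and Q10 are not among them.
- Prevalence of reactivity and the algorithm NPV follow from that classification and the test results, so they are untouched.
- The SAP 7.3 per-item NPV tests cover only the low-risk items, so they are untouched.
- Short-form selection (Protocol 8.4.1, SAP 7.3) and the protocol's NPV for each question can be affected.

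**5. Can the size be found?** Let e be the share with true earlier exposure, t the share of the remainder treated before answering, and b the share of those given a listed drug. The spurious share of Q9 yes answers is (1−e)tb / [e + (1−e)tb]. The documents give none of the three, so every input here is an assumption:

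| e | t | b | Spurious share of yes answers |
|---|---|---|---|
| 20% | 5% to 15% | 1 | 4/24 = 17% to 12/32 = 38% |
| 20% | 5% to 15% | 1/5 | 0.8/20.8 = 4% to 2.4/22.4 = 11% |
| 50% | 5% to 15% | 1/5 | 0.5/50.5 = 1% to 1.5/51.5 = 3% |

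A range of 1% to 38% shows that no estimate is available. For Q10 the drug class is irrelevant, so b = 1, but t then counts only subjects treated for those three infections.

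**6. What would contamination do to an item?** As an illustration, take the design's 3% prevalence and assume true earlier exposure in 50% of non-allergic and 10% of allergic subjects. Let a share f of the unexposed in both groups answer yes because of today's drug. Then P(yes) is 0.5 + 0.5f in the non-allergic and 0.1 + 0.9f in the allergic, and the NPV of a yes is 0.97·P(yes, non-allergic) / [0.97·P(yes, non-allergic) + 0.03·P(yes, allergic)].

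| f | P(yes), non-allergic | P(yes), allergic | NPV of a yes | Odds ratio |
|---|---|---|---|---|
| 0 | 0.500 | 0.100 | 99.39% | 9.0 |
| 2% | 0.510 | 0.118 | 99.29% | 7.8 |
| 5% | 0.525 | 0.145 | 99.15% | 6.5 |
| 10% | 0.550 | 0.190 | 98.94% | 5.2 |

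With 0.03 × 988 = 29.6 allergic subjects, f = 5% misrecords 0.05 × 0.9 × 29.6 = 1.3 of them, and f = 10% misrecords 2.7. These are small counts, but the selection step has only about 30 allergic subjects to learn from.

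**The case against.** The strongest reply is that the Q9 route is narrow. The subject must receive a listed antibiotic that day, receive it before the questionnaire, and count it when asked what they have ever taken since the reaction. Protocol 2.1 says that most providers do not routinely give B-lactams to patients who report penicillin allergy, and that such patients often receive second-line drugs. Section 4.1 admits patients attending for any reason, so many will need no STD drug. All of this stands, and it is why the point says that a drug can be recorded, not that it is. It limits Q10 less, because second-line treatment also produces a yes there.

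A second reply is that cases are recoverable. Concomitant medication is collected at the same visit (Protocol 6.1.2, Appendix A), and Q10 asks for the drug. That is partly right, but neither document plans to link those records to the two items.

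A third reply is that the low-risk marker in 2.1 belongs to other investigators and was not adopted in 6.1.2.1. This is correct, and it is one reason why the risk classification is unaffected.

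A reader might infer more than the documents support:
- That 17% to 38% of Q9 yes answers are spurious. This counts every treated subject as having received a listed drug, on assumed inputs.
- That the primary prevalence and NPV estimates are biased by these items. They do not use Q9 or Q10.
- That the oral challenge is left exposed to STD-drug side effects. Sections 4.1 and 6.3.4 name that problem and offer two ways to separate the two. It is a separate matter from the questionnaire.
- That item performance will differ by site. Workflow varies by site, so it could, but no data show that it does.

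**Conclusion.** The gap is real but narrow. The permitted order and the open wording of Q9 and Q10 together let a same-visit drug be recorded as past exposure, and no planned step would catch it. The reach is limited to choosing the 4-6 question form and, under the protocol's wording, the NPV for each question. The size is unknown. The figures above rest on assumed exposure and treatment shares, and the illustration also assumes that contamination is equally likely in allergic and non-allergic subjects. If clinicians give B-lactams more readily to some histories than to others, the direction could change. This is a low-cost improvement to data that serve a primary objective, not a threat to the main estimates.

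**What to change.** 1. In Appendix B, add the words 'before today's visit' to Q9 and to Q10. This alone removes the problem for subjects enrolled after the change.
2. On the concomitant medication CRF, flag any STD drug given at the same visit. For answers already collected, complete the flag from the existing medication records and the drug named in Q10, where these allow it.
3. In SAP 7.3, state in one sentence that a same-visit drug does not count as past exposure in the item-selection step, and how flagged answers under the old wording are handled.

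The cost is three words in each of two eCRF items, one CRF field, one SAP sentence and a marker for which wording each subject answered. The order of treatment and questionnaire can stay as it is, and clinical management does not change.
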